Sample Size and Power

Our preliminary data comparing the change in BMIz between WCV vs. **PRO WCV** yielded a difference of 0.05 units.⁶ This corresponded to an effect size (Cohen's d) of approximately 0.20 of a standard deviation. Additionally, based on our preliminary data and the literature, we estimate the intra-cluster correlation (ICC) to be 0.005 to account for the clustering of participant families within PCP. We recognize that participants may be lost to follow up during the course of the study or that we will not recruit equal number of participant families across all PCPs. Therefore, our sample size calculations further assume a coefficient of variation (COV) equal to 0.25 to account for this potential imbalance. This parameter being greater than 0 (i.e., equal sample size across clusters) increases the required sample size. Lastly, to account for two *a priori* statistical comparisons in Aim 1 (**WCV vs PRO WCV**, **WCV vs. PRO WCV + Food Care**), the significance level is set at 2.5%. **Table 2** reports the required sample size for enrollment under the stated assumptions. All calculations assume 80% power and an overall significance level of 5% such that each of the two comparisons will be made at the 2.5% significance level.

The software PASS v15 was used for all calculations, specifically the module for cluster randomized trials for two means. Table 2 reports the required sample size for enrollment under the above stated assumptions (reproduced in this response). We also varied the effect size to additionally include 0.25 and using 20 and 25 PCPs per arm to understand how varying-the

parameters affected the sample sizes. For example, assuming an effect size of 0.20, ICC of 0.005, COV of 0.25, 80% power, and 0.025 significance level, the study would be required to enroll 28 participant families per PCP per arm for a total of 560 families per arm. However, we further inflated the sample size to account for 7% of participants not receiving allocated treatment (i.e., WCV completed by a PCP in a different Arm than scheduled) and a 10% dropout at 1 year. This yields a sample size of 675 per arm or, with rounding, 33 families per each of 20 PCPs, for a total of 675 per arm (N=2,025 across all three arms).

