The study will have 80% power to detect an effect size of 0.20 with 20 PCPs per randomization arm and 33 participant families per PCP, for a total of 2,025 across all three groups in Aim 1. If we are able to obtain more PCPs, then we can reduce the number of families. Also, if the effect size is larger than we observed in our preliminary work,⁶ then the study will have > 80%. It is recognized that to assess for mediation and moderation that a larger sample size is required and thus, we do not expect to have a large power to detect these effects. Thus, Aim 2 results will be descriptive in nature. Given that multiple recruitment strategies are simultaneously in place, and the rate of enrollment is about 10 participants/week when 95% of the targeted sample has been achieved, the study has a buffer of 15 additional participants who may be in latter stages of recruitment when the sample is achieved. In other words, up to 2040 participants may be enrolled.

Outcomes

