take into account the clustered nature of the study design. To test the Aim 1 hypothesis that participants will have a lower change in BMIz (and secondarily, changes in BMI, BMI50, BMIz extended) in Arms 2 and 3, as compared to Arm 1, mixed linear models^{106,107} with restricted maximum likelihood estimation will be fit. The models will include a random effect for PCPs and will be assumed to follow a Gaussian distribution. These analyses will adjust for the stratification factors used in the randomization scheme and any baseline variables found to vary across intervention arms as identified above. Contrast statements will be written as functions of the estimated regression coefficients to estimate the effect of the interventions compared to standard WCV using a two-sided alpha of 0.025 to account for multiple testing. Model assumptions will be examined (e.g., QQ plots to assess normally distributed residuals) and of the underlying Gaussian random effect distribution. Secondary analyses will estimate the effectiveness of the interventions on the percent of children overweight and obese (≥ 85 percentile of BMI and ≥ 95 percentile of BMI) at 12 months. A similar strategy will be employed using a generalized linear mixed model assuming a binomial distribution for the outcomes. These models will treat the binary outcomes as measured from the 12-month visit. Analysis of secondary outcomes in Aims 1b and 1c (involvement in preventive care, parent and home factors) will follow the same strategy as described above. Due to lagging enrollment, the study modified data collection for secondary outcome in specific aim 1b- involvement in preventive care- just after 50% enrollment was reached. The timing of this outcome measure was changed from pre-visit only to pre- or -post visit to allow for families to enroll and complete baseline data collection after a completed WCV. As there are complementary analysis methods for cluster randomized trials, we will also fit Bayesian random effect models¹⁰⁸⁻¹¹⁰ for continuous and binary outcomes. Each model will use an inverse gamma prior for the cluster random effect variance parameter.¹¹¹ We will note any differences in the effect estimates across methods.

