Aim 2. The primary outcome variable is the same as in Aim 1, change in BMIz at 12 months. Aim 2 involves the assessment of mediating and moderating effects of PCP, parental and child behaviors (see list of variables in **Appendix B**). For a variable to be considered a mediator it must be associated with and in the casual pathway between the intervention and outcome. Therefore, we will first fit mixed linear models to each hypothesized mediator as dependent variables following the approach described in Aim 1. We will then fit similar models with BMIz as the outcome and each potential mediator as independent variable. Any variable found to be associated with intervention and BMIz will be considered a potential mediator variable. Our list of candidate mediator variables is measured at both the subject (parent and child) and cluster levels (PCP). To appropriately fit models with mediation at different levels we will rewrite the mixed models of Aim 1 as multilevel structure equation models (MSEM)¹¹² to include the variables in the analysis. Results will be expressed as total, direct, and indirect effects as estimated from the model. Moderation will be assessed using the MSEM framework.¹¹³ In Aim 1, we will also fit complementary Bayesian models to assess robustness of effect estimates. Aim 2 outcomes may be evaluated using secondary outcomes including raw BMI, BMI50, and BMIz extended.

Missing Data Considerations. We will minimize missing data by querying the EHR for anticipated and scheduled 1-year follow-up WCVs, sending reminders to each participant to schedule and attend appointment, and reminding participants of 1-year follow-up study questionnaires. Missing data, however, are inevitable in a longitudinal study due to dropout and

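### Aim 2, as most naturally read, admits pre-named mediators to the mediation model only after a two-step association screen on the same data; if that is a significance screen, weak mediators would often be lost and the indirect effects kept would be biased away from zero

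*Combined protocol and SAP*

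**What the plan says.** Aims 2a and 2b name the mediating constructs in advance: parent and PCP attitudes, norms, perceived control and intention, and child nutrition, activity, screen time and sleep. Appendix B assigns instruments to them.

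The Aim 2 paragraph of the Analytic Plan starts from the premise that a mediator has to be related to both intervention and outcome. It then sets an order of work. Each hypothesized mediator is first modelled on arm, by the Aim 1 method. BMIz is then modelled on each mediator. The rule that follows is: "Any variable found to be associated with intervention and BMIz will be considered a potential mediator variable". After that, the mixed models are recast as an MSEM, from which total, direct and indirect effects are reported.

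The paragraph gives no threshold for association, no sample split, no correction for selection, and no statement of what is reported for a variable that fails either step.

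Sample Size and Power says that mediation and moderation need a larger sample than planned and that large power is not expected. Its conclusion is: "Thus, Aim 2 results will be descriptive in nature".

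**The concern.** A descriptive aim reports each estimate with its uncertainty, whatever its size. A double screen on the same data withholds estimates according to their size. The two passages therefore pull in opposite directions, and the plan's own expectation of low power marks the setting in which a screen does most harm.

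Two things are at stake. A mediator that fails may be taken for one that does not mediate, when the failure may only reflect imprecision. And a product of two coefficients, each kept because it was large enough, overstates the true product on average. The Outcomes section says the mediating pathways were chosen to inform steps that parents and PCPs can take together, so the relative size of the reported pathways matters to their intended use.

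**Working it through.** **The plan's own figure.** The documents give no power figure for Aim 2, so I reproduced Aim 1 first to fix the precision available. Inputs, from Sample Size and Power: "assuming an effect size of 0.20, ICC of 0.005, COV of 0.25, 80% power, and 0.025 significance level"; the Aim 2 models follow the Aim 1 approach, which tests "using a two-sided alpha of 0.025 to account for multiple testing".

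- Unclustered n per arm = 2 × ((z₀.₉₈₇₅ + z₀.₈₀)/0.20)² = 475.3.
- Design effect at 28 per PCP = 1 + ((0.25² + 1) × 28 − 1) × 0.005 = 1.144.
- 475.3 × 1.144 = 543.7, and 28 is the smallest whole number per PCP that suffices with 20 PCPs: 28 × 20 = 560. The plan says "enroll 28 participant families per PCP per arm for a total of 560 families per arm", an exact match. 560/(1 − 0.17) = 675 also matches.

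**Assumptions the documents do not supply.** Path sizes in SD units (a = arm to mediator, b = mediator to BMIz change); association means p < 0.05 at each step, with 0.025 as a variant; unit variances; two arms compared unless stated.

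**Standard errors for participant-level mediators.** Two sample sizes are used: 560 per arm with design effect 1.144, and 607 per arm (675 × 0.90 = 607.5) with design effect 1 + (1.0625 × 30 − 1) × 0.005 = 1.15. At 607:

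- SE(a) = √(2 × 1.15/607) = 0.0616
- SE(b) = 1/√1214 = 0.0287

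**Pass rate and inflation.** With the two estimates drawn independently, the pass rate is the product of the two powers. For a = b = 0.10 at 607 per arm and 0.05, the powers are 0.369 and 0.936, so 0.369 × 0.936 = 0.35. Inflation is the mean of a-hat × b-hat among passing draws, divided by a × b.

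| a / b | 607, p<0.05 | 560, p<0.05 | 560, p<0.025 |
|---|---|---|---|
| 0.10 / 0.10 | 35%, 1.7× | 32%, 1.8× | 22%, 1.95× |
| 0.15 / 0.05 | 28%, 1.9× | 25%, 2.0× | 15%, 2.25× |
| 0.10 / 0.05 | 15%, 2.5× | 13%, 2.7× | 7%, 3.1× |
| 0.20 / 0.10 | 84%, 1.1× | 81%, 1.1× | 70%, 1.2× |
| 0.30 / 0.20 | 100%, 1.0× | 100%, 1.0× | 99%, 1.0× |

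Without a screen the ratio is 1.0 in every row.

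**Cross-check.** A full cluster simulation (two arms, 20 PCPs × 28 families, ICC 0.005, 2,000 runs per case, b negative) gave 32% and 1.75× for 0.10/0.10, 13% and 2.55× for 0.10/0.05, 82% and 1.14× for 0.20/0.10, and 100% and 1.00× for 0.30/0.20, all at 0.05. Unscreened means were 0.95 to 1.02 times the truth.

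**Three-arm version.** If b is estimated on all three arms (607 × 3 = 1,821 children), a is equal in both active arms and either arm can satisfy the first step, the first three rows at 607 per arm and 0.05 become 52%/1.4×, 47%/1.5× and 30%/1.8×.

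**PCP-level mediators.**

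- First step: a 0.5 SD arm shift with 20 PCPs per arm has SE √(2/20) = 0.316 and passes about 35% of the time at 0.05.
- Second step: with ICC 0.005, a PCP variable explaining a quarter of between-PCP variance has slope √(0.005/4) = 0.035. Its SE is √((0.005 + 0.995/30)/60) = 0.025, so it passes about 29% of the time.
- In the cluster simulation, a = 0.5, b = −0.10 passed 32% with 1.70×, and a = 0.8, b = −0.10 passed 66% with 1.23×. A slope of 0.10 implies 0.10² = 0.01 of between-PCP variance, twice the planning ICC, so these two cases favour passing.

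**The case against.** The strongest reply is that the plan does not say what the concern needs it to say. A variable that passes is called a potential mediator, the next sentence speaks of the list of candidates, and the MSEM is built to include the variables in the analysis, which could mean the whole list. No sentence excludes a failed variable, and no cut-off exists. This stands as a limit. The exclusion is the most natural reading of the sequence, because the screen has no other evident purpose, but it is still a reading, and the numbers depend on an assumed cut-off.

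Second, the weak cases are small by construction. Against the 0.20 SD design effect, products of 0.010, 0.0075 and 0.005 carry 5%, 3.75% and 2.5% of it. Stronger mediators are barely affected, and three-arm models soften the result. This also stands. A strong b path alone does not remove the bias, however: a = 0.10, b = 0.20 still gives 37% and 1.6× at 607 per arm.

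Three stronger inferences are tempting, and the documents do not support them:

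- A reader might infer that the plan drops true mediators and inflates the rest as a matter of course. Both effects depend on the cut-off and the path sizes.
- A reader might infer that arm is left out of the mediation model. Direct and indirect effects cannot be reported without arm in the MSEM outcome equation. Only its presence in the second screening step is unstated.
- A reader might infer that removing the screen would recover the missed mediators. At 607 per arm, a 95% Monte Carlo interval for the unscreened indirect effect excludes zero 31%, 27% and 12% of the time in the three weak cases, no more often than the screen passes them. Low detection is a sample-size limit that the plan discloses.

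The descriptive label lowers the stakes, but it does not remove selection bias from the indirect effects that are printed.

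**Conclusion.** The concern holds in conditional form. The Aim 2 text, most naturally read, applies a same-data screen that conflicts with the low-power, descriptive status the plan gives Aim 2. If association means significance at 0.05, participant-level mediators with assumed paths of 0.05 to 0.15 SD survive about 13-35% of the time with about 1.7-2.7 times inflation in a two-arm comparison, or about 30-52% with 1.4-1.8 times under three-arm models in which either arm can pass. Using the Aim 1 level of 0.025 would worsen this. PCP-level mediators with modest arm shifts are in a similar position. For strong mediators the bias is about 1.1 times (0.20/0.10) or nil (0.30/0.20).

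The part specific to the screen is the selection bias in reported indirect effects. The low power is not caused by it. The issue is confined to a secondary aim, and the primary Aim 1 analysis is untouched.

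**What to change.** In the Aim 2 paragraph, delete association with arm and BMIz as a condition for entering the MSEM. For every mediator named in Aims 2a and 2b, fit the mediation model with arm in the outcome equation. Report the a path, the b path and the indirect effect, each with a confidence interval and regardless of significance, and label them descriptive, in line with Sample Size and Power. If the intention was always to model all candidates, one sentence saying so settles the point.

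The cost is SAP wording and a longer results table; no new data are needed. The change removes the selection bias in the reported indirect effects. It does not raise the power to detect mediation, and the text should not suggest that it does.

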The primary child-level outcome is the 1-year difference in change in BMIz between study arms using World Health Organization growth reference standards. BMI values will be obtained from Geisinger clinical care visits, documented in the EHR. Values obtained at well child visits (preferred), clinical visits, or self-report during the study period, ideally 12 months, 1 day apart will be utilized but values from baseline WCV to 9 to 18 month follow-up may be used to assess the primary outcome. This primary outcome is chosen because it reflects the difference in the effectiveness of each intervention versus standard of care in preventing obesity among a high-risk population of preschool-aged children. The difference in the difference between groups is chosen because the intervention is randomized at the PCP and not the patient-level. Parent self-report of child weight and height is added to supplement primary outcome data given unprecedented changes in pediatric care secondary to the pandemic. Specifically, the availability of WCVs has decreased due to staff turnovers yet the demand has decreased as families delay or forgo preventive care. To optimize follow-up height and weight data collection, parents of children without a clinical BMI at about 1-year post-baseline WCV, will be encouraged to complete the child's follow-up WCV, per clinical schedule, or to visit the clinic for height and weight measures. Among this subset of the study population (implemented in September 2022), parent self-reported data about child's height and weight will be collected before the WCV or clinic visit.¹⁵³⁻¹⁵⁶ Parents will be asked whether the self-reported data are estimates or measured at home.¹⁵³⁻¹⁵⁶ Among a smaller subset, the self-reported data will be compared with objective height and weight collected in usual clinical care. Concordance between the parent self-report and clinical measures will be evaluated for validation of self-reported data. If the variation among self-report with objective clinical measures is acceptable, self-reported data may be used as follow-up measures. To determine if the variation is acceptable, variation will be compared to the literature to inform analytical strategies for using supplemental parent-reported data in the absence of clinical measures.¹⁵³⁻¹⁵⁶ The use of self-reported measures is anticipated for studies

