nonresponse to study questionnaire items. We anticipate that no more than 7% of randomized subjects will not receive allocated treatment and 10% of randomized subjects will fail to complete the study;^{63,90,115} but reasons for loss at point of WCV care and dropout will be documented. Before proceeding with primary analyses, we will characterize patterns of missingness using exploratory analyses to provide insights into how to handle the missing data. Participants with missing data will be compared to participants with complete data to ensure there are no differences. Depending on the amount of missing data, we will use a non-parametric missing data imputation method based on random forests.¹¹⁶ This method has been shown to perform as well as or better than more traditional methods of imputation, and it has the advantage of imputing both continuous and categorical data. By using random forests, we can capture non-linear relationships and interactions present in the dataset that may otherwise be missed when using a different method. At least 5 complete datasets will be created and combined using the methods of Rubin.¹¹⁷

Heterogeneity of treatment effect (HTE). HTE analyses are incorporated into Aim 2 when examining moderator effects. Additional sub-group analyses will be performed by child sex (males, females) and baseline BMI weight category (overweight, obese). These sub-group analyses will employ the same models as described in Aim 2.

Aim 3. The **RE-AIM framework**²⁹ will be used to evaluate the interventions' reach to the target population and subgroups (e.g., by provider type, those with food insecurity and hunger), comparative effectiveness, adoption by PCPs, implementation fidelity and barriers, and maintenance of intervention components over time, so as to inform translation of this study into practice.

EXPECTED RISKS/ BENEFITS

Potential Risks

The greatest potential risk to participants in this research is a loss of confidentiality. To minimize the risk of loss of confidentiality, all data collected as part of this study will be stored on the Geisinger password-protected network only accessible to IRB-approved study staff. Participants will also be assigned a unique study ID for data collection. In the event that any data would be shared outside of Geisinger, it would be done using an IT-approved secure transport method to ensure data security is maintained.

Benefits

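### Random-forest imputation pooled by Rubin's rules with no draw step described: if applied to 12-month BMIz, the standard error can be too small and the effect can be attenuated

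*Combined protocol and SAP*

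**What the plan says.** The relevant text is the Missing Data Considerations paragraph of the Analytic Plan in the combined protocol and SAP.

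- Method: "Depending on the amount of missing data, we will use a non-parametric missing data imputation method based on random forests".
- Pooling: "At least 5 complete datasets will be created and combined using the methods of Rubin".
- Timing: "Before proceeding with primary analyses, we will characterize patterns of missingness using exploratory analyses to provide insights into how to handle the missing data".
- Expected loss: "10% of randomized subjects will fail to complete the study".
- Scope: the paragraph opens with "We will minimize missing data by querying the EHR for anticipated and scheduled 1-year follow-up WCVs" and continues "Missing data, however, are inevitable in a longitudinal study due to dropout". It then also names "nonresponse to study questionnaire items".

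The paragraph does not say how the five datasets come to differ, which variables are imputed, which predictors enter the forest, or how much missing data triggers imputation. The Outcomes section allows BMI gaps to be filled from other clinic visits, from a 9 to 18 month window and, if agreement is acceptable, from parents: "Parent self-report of child weight and height is added to supplement primary outcome data given unprecedented changes in pediatric care".

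The forest sentence cites reference 116 and the pooling sentence 117. As listed, 116 is a multiple-imputation overview and 117 a paper on natural gas development and birth outcomes. Citations in this part of the text run one ahead of the list: cluster CONSORT is cited as 104 and listed as 103, and the variance-prior paper is cited as 111 and listed as 110. Shifted by one, the forest reference is entry 115 (MissForest), whose title closely matches the plan's description, and the pooling reference is the multiple-imputation overview.

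**The concern.** Rubin's rules add the between-imputation variance B to the average within-imputation variance W. B reflects the uncertainty about the missing values only if each dataset contains a random draw from their predictive distribution. A regression forest returns a mean. Five forests with different seeds return nearly the same mean, so B is close to zero, and the filled-in children count as observed while showing almost no residual scatter.

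If this is done to the primary outcome, two things can go wrong. Where arm strongly determines the fill-in, the standard error is too small and the test exceeds its level. Where arm has little or no influence, filled-in children in all arms receive similar values and the estimated difference is pulled towards zero. The trial targets a small effect (d = 0.20) with alpha split to 0.025 per comparison, so both matter.

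**Working it through.** **The plan's own figure.** Inputs from Sample Size and Power: d = 0.20, two-sided alpha 0.025, power 80%, ICC 0.005, COV 0.25, 20 PCPs per arm.

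- Unclustered n per arm = 2 × ((2.2414 + 0.8416)/0.20)² = 475.3.
- Design effect with 28 per PCP = 1 + ((1 + 0.25²) × 28 − 1) × 0.005 = 1.144. Required n = 475.3 × 1.144 = 544, which 20 × 28 = 560 covers; 27 per PCP (540 against 541 required) does not.
- 560/(1 − 0.17) = 674.7, so 675.

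The plan's figures reproduce. It gives no figure for the precision of the imputed analysis.

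**Limit 1: arm fully used, no draw.** Let f be the missing share and n the number per arm, with outcome SD 1. Each missing value is replaced by its arm's observed mean.

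- True variance of an arm mean: 1/(n(1 − f)).
- Reported variance: (1 − f)/n, because the filled-in values have no scatter.
- Reported SE / true SE = 1 − f.
- Type I error = 2Φ(−2.241(1 − f)): 0.0437 at f = 0.10, 0.0332 at f = 0.05 (an assumed lower share) and 0.073 at f = 0.20 (an assumed higher share).

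**Limit 2: arm not used, no draw.** Missing values in all arms receive a common mean.

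- Estimate = (1 − f) × observed difference, so 0.20 becomes 0.18 at f = 0.10.
- True variance of the difference: (1 − f)² × 2/(n(1 − f)) = 2(1 − f)/n, which equals the reported variance.
- SE ratio is 1 and type I error stays at 0.025. The z statistic equals that of the observed outcomes, so the harm is a biased estimate and interval, not a false level.

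**Simulation A.** From the plan: three arms of 675, 20 PCPs per arm, ICC 0.005, COV 0.25, REML model with random PCP effect, five imputations. Assumed: missing completely at random, covariate R² 0.1, two strata, 100 trees, 2 features per split, minimum leaf 5; 3,000 runs, except 40,000 for the linear row. SE/SD is relative to full data.

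**Simulation B.** Two arms, 20 PCPs × 33, ICC 0.005 treated as known, missing completely at random, 50 trees, one forest per run because B was near zero; 1,500 runs.

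Results at 10% missing under the null, with Monte Carlo SE in percentage points:

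| Imputation | SE/SD | Type I error |
|---|---|---|
| A: full data | – | 2.57% (0.21) |
| A: one forest, arm a predictor | 0.933 | 3.55% (0.25) |
| A: one forest per arm | 0.910 | 4.05% (0.27) |
| A: arm-specific linear prediction, no draw | – | 4.28% (0.08) |
| A: bootstrap forest with random donors | 0.994 | 2.28% (0.20) |
| B: forest, arm + 2 covariates | 0.933 | 3.1% (about 0.4) |
| B: forest, arm + 10 covariates | 0.979 | 2.6% (about 0.4) |

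- Between-imputation variance: in A, B/W was 0.0006–0.0008 without draws against 0.097 with donors. In B, 1.2B/T (T the total variance) was about 0.002 in 20 pilot runs, against about 0.09 with proper draws.
- Pooled SE in A: 0.0565, below both 0.0596 (no outcome missing) and 0.0624 (observed outcomes only). 0.0565/0.0624 = 0.905, in line with limit 1.
- Other forest settings in A (500 runs each): SE ratios 0.908–0.953, giving 0.033–0.042 by normal approximation, not by counting.
- At 20% missing in B: 5.5% with 2 covariates, 6.6% by arm, 2.8% with 10 covariates.
- Effect at d = 0.20 in A (120 runs each), relative to full data: 0.983 joint forest, 1.005 by arm, 0.903 with arm omitted. A rough unclustered run with arm among 31 predictors gave about 0.94.

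**The case against.** The strongest reply is that creating several datasets and pooling them by Rubin's rules describes multiple imputation, with forests as the model. A draw is not excluded, and the Analytic Plan promises a data management plan and a statistical analysis plan at start-up, where such mechanics could sit. This stands in part: the documents do not show that a prediction-only method will be run. But this text states the imputation method and the pooling rule, and nothing in it makes the pooling valid.

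Three stronger readings are tempting, and the documents do not support them.

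- A reader might infer that the cited method is known to lack draws. The bibliography gives only its title, and reaching that title needs the one-number shift. The point rests on the absence of a described draw step, not on the citation.
- A reader might infer that type I error necessarily exceeds 0.025. With arm among 11 predictors the count was 2.6%, indistinguishable from nominal. The plan lists 21 factors and 156 baseline parent items, so a forest with many predictors is plausible. Attenuation is then the larger harm, even with arm included.
- A reader might infer that 12-month BMIz will certainly be imputed. The opening on 1-year visits, the mention of dropout and the link to primary analyses imply it. Questionnaire nonresponse is also named, the trigger is open, and the back-up BMI sources could leave fewer than 10% missing.

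**Conclusion.** The point holds in conditional form and should be corrected before analysis. As written, the plan pools forest imputations by Rubin's rules without a step that would give the pooling anything to measure. If predictions are filled in for 12-month BMIz, then at 10% missing the type I error per comparison lies between about 0.026 and about 0.044 against 0.025. The SE ratio lies between about 0.98 and 0.90 over the same range. Where arm is diluted or omitted, the effect shrinks by up to about 10%, for example from 0.20 to 0.18. The plan does not say which predictors enter, so it does not say which harm would apply.

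These sizes assume no draw step, use on the primary outcome, imputation being triggered, and data missing completely at random. The 10% is the plan's dropout figure; the share of missing BMIz may be lower or higher, and the error grows with it. The unstated trigger and the unstated order of back-up BMI values are missing detail, not errors in themselves.

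**What to change.** In Missing Data Considerations, replace the forest sentence with a multiple-imputation procedure that includes a draw. Suitable choices are forests grown on bootstrap samples with random donors from terminal nodes, or a multilevel parametric model with parameter and residual draws. Put arm (or impute separately by arm), PCP, the stratification factors and baseline BMIz in the imputation model. PCP belongs there because it is the unit of randomisation and the random effect in the analysis model. Report the already planned REML mixed model on observed outcomes alongside.

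While editing, state whether 12-month BMIz is imputed, where imputation falls relative to the back-up BMI sources, and what amount of missing data triggers it. Correct the two reference numbers.

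The cost is SAP wording and minor programming. Intervals become wider than the prediction-only ones: at 10% missing the SE is about 0.062 instead of 0.0565, roughly a tenth more. In simulation A the donor-draw forest brought type I error back to 2.3% (Monte Carlo SE 0.2) with no shrinkage of the effect (ratio 1.00). In simulation B, proper parametric draws gave 3.0%, 2.5% and 3.1% at 10%, 20% and 30% missing (Monte Carlo SE about 0.3).

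### The random-forest imputation is not tied to arm: one forest over all arms would shrink the primary BMIz contrast by about 5–10% at the planned 10% dropout

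*Combined protocol and SAP*

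**What the plan says.** Under Analytic Plan, Missing Data Considerations, the plan first explores patterns of missingness and then states: "Depending on the amount of missing data, we will use a non-parametric missing data imputation method based on random forests". At least five completed datasets are to be combined by Rubin's rules. The reason given for the method is: "By using random forests, we can capture non-linear relationships and interactions present in the dataset that may otherwise be missed".

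The section does not state:
- whether the forest is fitted across arms or within arm
- whether arm or PCP is a predictor
- whether 12-month BMIz or its change is imputed
- how values are drawn
- how much missing data triggers imputation

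The Analytic Plan opens by promising a statistical analysis plan during start-up, but the text supplied gives no further detail on imputation and no sensitivity analysis to the imputation model.

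The effect to be protected is in Sample Size and Power. The preliminary comparison "yielded a difference of 0.05 units" of BMIz, described as "approximately 0.20 of a standard deviation". The Aim 1 analysis is a REML mixed linear model of change in BMIz with a random PCP effect. Each active arm is compared with Arm 1 "using a two-sided alpha of 0.025 to account for multiple testing".

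**The concern.** A regression forest chooses splits by how much they reduce prediction error. An arm effect of 0.2 SD is a weak predictor, and it competes with baseline BMIz and with the questionnaire and demographic variables listed in Appendix B. A forest pooled over arms will often not split on arm, and cannot do so if arm is not supplied. Children with missing outcomes in different arms then receive imputed values that are too alike, and on average the completed-data contrast is pulled toward zero.

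This is a bias in the point estimate, separate from whether the standard error is right. Adding a random draw to each imputed value does not restore an arm difference that the forest never learned. The two primary comparisons, Arm 2 and Arm 3 against Arm 1, are what is at stake.

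**Working it through.** **Inputs from Sample Size and Power and from Aim 1.** Difference 0.05 BMIz and d = 0.20, so the implied SD of change is 0.05/0.20 = 0.25. Two-sided alpha is 0.025 per comparison and power 80%. Clustering: "we estimate the intra-cluster correlation (ICC) to be 0.005", and a "coefficient of variation (COV) equal to 0.25" for cluster size. There are 20 PCPs per arm, 560 families per arm before inflation, and 675 enrolled. Dropout is 10%, repeated in Missing Data Considerations.

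**1. Reproduce the plan's sample size.**
- Without clustering: n = 2(2.241 + 0.842)²/0.20², which gives 476 per arm.
- Design effect at m = 28: 1 + [(1 + 0.25²) × 28 − 1] × 0.005 = 1.144.
- 476 × 1.144 ≈ 544, and 544/20 = 27.2, so 28 per PCP and 28 × 20 = 560. Normal-approximation power at 560 is 81.3%.
- Inflation: 560/(1 − 0.07 − 0.10) = 674.7, so 675.

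The plan's figures are reproduced.

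**2. Dilution formula.** Let f be the share of outcomes imputed and r the share of the arm effect kept in the imputed values. The average contrast after imputation is

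δ × [1 − f(1 − r)],

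so the proportional shrinkage is f(1 − r), which for r between 0 and 1 cannot exceed f.

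**3. Simulated r.** 60 PCPs × 34 children, a 0.05 arm effect, 10% of outcomes missing completely at random, forests of 100 trees, 20 runs per setting. These settings are assumptions, not in the documents: baseline BMIz SD 0.8; 10 or 25 further covariates, two of them weakly prognostic; node size 5; √p or p/3 variables tried per split; missing completely at random.

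**4. Power.** At 10% missing, 675 × 0.90 = 607.5 per arm, or 30.4 per PCP. The design effect is 1 + (1.0625 × 30.375 − 1) × 0.005 = 1.156. The SE of d is √(2 × 1.156/607.5) = 0.0617. Undiluted power is Φ(0.20/0.0617 − 2.241) = Φ(1.00) = 84.1%. With r = 0 it is Φ(0.18/0.0617 − 2.241) = Φ(0.68) = 75.0%. This treats properly drawn imputations as adding no information beyond the observed children.

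| How the forest is run | r | Simulated contrast ÷ complete-case contrast | Contrast from formula, f = 0.10 | Power |
|---|---|---|---|---|
| Pooled, arm not a predictor | about 0 | 0.897–0.913 | 0.0450 | 75.0% |
| Pooled, arm included, 12-month BMIz imputed | 0.09–0.27 | 0.907–0.931 | 0.0455–0.0464 | 76.0–77.7% |
| Pooled, arm included, change imputed | 0.34–0.52 | 0.928–0.955 | 0.0467–0.0476 | 78.4–80.1% |
| Separate forest in each arm | about 1 | 0.983–1.007 | 0.050 | 84.1% |

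The simulation standard error of the ratios is 0.004 to 0.022. Every pooled setting attenuates the contrast. Separate forests by arm show essentially none.

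**5. Scale against sampling error.** The SE of the contrast is 0.25 × 0.0617 = 0.0154 BMIz. A bias of 0.0025–0.005 is therefore about 0.16–0.32 SE.

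**6. If more is missing.** At 20%, an assumed figure, the contrast for r between 0 and 0.52 is 0.040–0.045 and power is 59–71%, against 79.9% undiluted.

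**The case against.** The strongest reply is that the plan never says it will fit one forest across arms. That is right. A reader might infer a stated pooled fit from the phrase about relationships in the dataset, or from the MissForest entry in the bibliography, but neither settles how arm is handled. Pooling is the natural reading of a silent text, and the point stands only on that condition.

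Imputation is also conditional and has no stated trigger. The same paragraph covers unanswered questionnaire items, so the forest may be used mainly for those. The Outcomes section limits outcome loss by accepting measurements at 9 to 18 months and possibly parent report. All of this stands. But because imputation depends on the amount missing, it is most likely to be used where dilution is largest. The Outcomes section also reports that families were delaying or forgoing preventive care.

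The size is modest at 10% missing, and it is an average over imputed children, not a pull exerted by each one. That stands too. The power loss requires imputations with proper variance. If the five datasets were only repeated forest mean predictions, the standard error would shrink with the estimate. With r = 0 the test statistic would then be roughly unchanged, and the harm would be a biased estimate with too narrow an interval.

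Finally, the mixed model on observed outcomes is not automatically better. With one change score per child it is a complete-case analysis that conditions only on its own covariates, whereas a forest can use more, such as the 6-month questionnaires.

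**Conclusion.** The point holds as a conditional one. If a single forest over all arms is used to impute the primary outcome, the arm contrast is biased toward zero. At the planned 10% dropout the average shrinkage is about 5–10%, from 0.050 to 0.045–0.048 BMIz. Power falls from about 84% to about 75–80% when imputations carry proper variance. The values of r rest on the simulation assumptions listed above; the ceiling, that shrinkage cannot exceed the share imputed, does not.

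Three stronger readings are not supported:
- **That imputed outcomes carry almost none of the arm effect.** This is fair when arm is left out or 12-month BMIz is imputed. The named primary variable is change in BMIz, and when change is imputed with arm included a third to a half of the effect is kept.
- **That 17% of outcomes will be missing.** This would add the 7% seen by a PCP in another arm to the 10% dropout. Study Procedures keeps those children in the intent-to-treat analysis, so the planned missing share is 10%.
- **That the observed-data mixed model avoids the bias under the same missing-at-random assumption.** It conditions on fewer variables, so the assumption differs.

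**What to change.** Add to Missing Data Considerations that whenever the primary outcome is imputed, the random-forest imputation is run separately within each randomised arm. Report the REML mixed model fitted to observed outcomes alongside it as a sensitivity analysis. The same addition should name the variable imputed (change or 12-month BMIz), the trigger, how values are drawn and how PCP enters, since the bias and the interval depend on these choices.

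The cost is a sentence or two, the same code run three times, and slightly noisier forests because each is grown on about 600 observed children (675 × 0.90 = 607.5) instead of about three times as many. The text should be settled before any analysis by arm, so that the choice cannot be influenced by the result.
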